8.3.8 Adverse events of special interest

Adverse events of special interest (AESIs) are events of scientific and medical interest specific to the further understanding of the acalabrutinib safety profile and require close monitoring and rapid communication by the investigators to the sponsor. An AESI can be serious or non-serious.

All AESIs will be recorded and reported to the sponsor or designee within 24 hours. The investigator will submit any updated AESI data to the sponsor within 24 hours of it being available. Serious AESIs will be recorded and reported as per Section [8.4.1](#).

The following events are AESIs for subjects who receive acalabrutinib and must be reported to the sponsor expeditiously irrespective of regulatory seriousness criteria or causality:

- Ventricular arrhythmias (e.g., ventricular extrasystoles, ventricular tachycardia, ventricular arrhythmia, ventricular fibrillation, etc.)

8.3.9 Hy's law

Cases where a subject shows elevation in liver biochemistry may require further evaluation and occurrences of AST or ALT $\geq 3 \times \text{ULN}$ together with total bilirubin $\geq 2 \times \text{ULN}$ may need to be reported as SAEs. Please refer to [Appendix D](#) for further instruction on cases of increases in liver biochemistry and evaluation of Hy's Law.

8.3.10 Disease progression

Disease progression can be considered as a worsening of a subject's condition attributable to the disease for which the investigational product is being studied. It may be an increase in the severity of the disease under study and/or aggravation in the symptoms of the disease. The development of new, or progression of existing metastasis to the primary cancer under study should be considered as disease progression and not an AE. **Events, which are unequivocally due to disease progression, should not be reported as an AE during the study.**

8.3.11 New cancers

The development of a new cancer should be regarded as an AE and will generally meet at least one of the serious criteria. New primary cancers are those that are not the primary reason for the administration of the study treatment and have been identified after the patient's inclusion in this study. They do not include metastases of the original cancer.

8.3.12 Handling of deaths

All deaths that occur during the study, or within the protocol-defined follow-up period after the administration of the last dose of investigational product, should be reported as follows:

- Death, which is unequivocally due to disease progression, should be communicated to the study monitor at the next monitoring visit and should be documented in the eCRF module, but should not be reported as a SAE during the study
- Where death is not due (or not clearly due) to disease progression of the disease under study, the AE causing the death should be reported to the study monitor as an SAE within 24 hours. The report should contain a comment regarding the co-involvement of progression of disease, if appropriate, and should assign a single primary cause of death together with any contributory causes
- Deaths with an unknown cause should always be reported as a SAE but every effort should be made to establish a cause of death. A post-mortem may be helpful in the assessment of the cause of death, and if performed a copy of the post-mortem results (with translation of important parts into English) should be reported in an expedited fashion to an AstraZeneca representative within the usual timeframes.

Deaths occurring after the protocol-defined reporting period (30 days after the last dose of study treatment) should be documented in the Death page. If the death occurred as a result of an event that started after the defined follow-up period and the event is considered to be due to a late-onset toxicity to study treatment, then it should also be reported as an SAE.

8.4 Safety reporting and medical management

8.4.1 Reporting of serious adverse events

All SAEs have to be reported, whether or not considered causally related to the investigational product, or to the study procedure(s). All SAEs will be recorded in the CRF.

If any SAE occurs in the course of the study, then Investigators or other site personnel inform the appropriate AstraZeneca representatives within one day i.e., immediately but **no later than 24 hours** of when he or she becomes aware of it.

The designated AstraZeneca representative works with the Investigator to ensure that all the necessary information is provided to the AstraZeneca Patient Safety data entry site **within 1**

calendar day of initial receipt for fatal and life-threatening events **and within 5 calendar days** of initial receipt for all other SAEs.

For fatal or life-threatening adverse events where important or relevant information is missing, active follow-up is undertaken immediately. Investigators or other site personnel inform AstraZeneca representatives of any follow-up information on a previously reported SAE within one calendar day i.e., immediately but **no later than 24 hours** of when he or she becomes aware of it.

Once the Investigators or other site personnel indicate an AE is serious in the EDC system, an automated email alert is sent to the designated AstraZeneca representative.

If the EDC system is not available, then the Investigator or other study site staff reports a SAE to the appropriate AstraZeneca representative by telephone.

The AstraZeneca representative will advise the Investigator/study site staff how to proceed.

For further guidance on the definition of a SAE, see [Appendix B](#) of the Clinical Study Protocol.

8.4.2 Pregnancy

All pregnancies and outcomes of pregnancy should be reported to AstraZeneca except for: If the pregnancy is discovered before the study subject has received any study drug.

If a pregnancy is reported, the investigator should inform the sponsor within 24 hours of learning of the pregnancy.

Abnormal pregnancy outcomes (e.g., spontaneous abortion, fetal death, stillbirth, congenital anomalies, ectopic pregnancy) are considered SAEs.

8.4.2.1 Maternal exposure

If a subject becomes pregnant during the course of the study, investigational product should be discontinued immediately.

Pregnancy itself is not regarded as an adverse event unless there is a suspicion that the investigational product under study may have interfered with the effectiveness of a contraceptive medication. Congenital anomalies /birth defects and spontaneous miscarriages should be reported and handled as SAEs. Elective abortions without complications should not be handled as AEs. The outcome of all pregnancies (spontaneous miscarriage, elective termination, ectopic pregnancy, normal birth or congenital anomaly) should be followed up and documented even if the subject was discontinued from the study.

If any pregnancy occurs during exposure to investigational product and until 2 days after the last dose of acalabrutinib, then the Investigator or other site personnel informs the appropriate AstraZeneca representatives within 1 day i.e., immediately but **no later than 24 hours** of when he or she becomes aware of it.

The designated AstraZeneca representative works with the Investigator to ensure that all relevant information is provided to the AstraZeneca Patient Safety data entry site within 1 or 5 calendar days for SAEs (see Section 8.4.1) and within 30 days for all other pregnancies.

The same timelines apply when outcome information is available.

The PREGREP module in the CRF is used to report the pregnancy and the PREGOUT is used to report the outcome of the pregnancy.

8.4.2.2 Paternal exposure

Pregnancy of the participant's partner is not considered to be an AE. However, the outcome of all pregnancies (spontaneous miscarriage, elective termination, ectopic pregnancy, normal birth, or congenital abnormality) occurring from the date of the first dose of study intervention until 2 days after the last dose of acalabrutinib, should be followed up and documented in the medical record and provided to the sponsor Patient Safety data entry site. Consent from the partner must be obtained before the information is collected and reported to AstraZeneca.

Where a report of pregnancy is received, prior to obtaining information about the pregnancy, the investigator must obtain the consent of the participant's partner. The local study team should adopt the Master Pregnant Partner Form in line with local procedures/requirements and submit it to the relevant Regulatory Authority/IRBs/IECs prior to use.

8.4.3 Overdose

For this study, any dose of acalabrutinib greater than the dose being studied will be considered an overdose. However, if acalabrutinib is administered with strong CYP3A inducers, the recommended dose is 200mg BID (Table 6). It is not considered as overdose in this situation. Avoid co-administration of strong CYP3A inducers with acalabrutinib.

For any subject experiencing an acalabrutinib overdose, observation for any symptomatic side effects should be instituted, and vital signs, biochemical and hematologic parameters, and ECGs should be followed closely (consistent with the protocol or more frequently, as needed). Appropriate supportive management to mitigate adverse effects should be initiated. If the overdose ingestion is recent and substantial, and if there are no medical contraindications, use of gastric lavage or induction of emesis may be considered.

Such overdoses should be recorded as follows:

- An overdose with associated AEs is recorded as the AE diagnosis/symptoms on the relevant AE modules in the CRF and on the Overdose CRF module.
- An overdose without associated symptoms is only reported on the Overdose CRF module

If an overdose on an IMP/study intervention occurs in the course of the study, then the investigator or other site personnel inform appropriate AstraZeneca representatives immediately, or **no later than 24 hours** of when they become aware of it.

The designated AstraZeneca representative works with the Investigator to ensure that all relevant information is provided to the AstraZeneca Patient Safety data entry site within one or 5 calendar days for overdoses associated with a SAE (see Section 8.3.2), and within 30 days for other overdoses

8.4.4 Medication Error, Drug Abuse, and Drug Misuse

If an event of medication error, drug abuse, or drug misuse occurs during the study, then the investigator or other site personnel informs the appropriate AstraZeneca representatives within 1 calendar day i.e., immediately but no later than 24 hours of when they become aware of it.

The designated AstraZeneca representative works with the investigator to ensure that all relevant information is completed within **1** (initial fatal/life-threatening or follow up fatal/life-threatening events) or **5** (other serious initial and follow up events) **calendar days** if there is an SAE associated with the event of medication error, drug abuse, or misuse (see Section 8.3.2) and **within 30 days** for all other medication errors.

8.4.4.1 Medication Error

For the purposes of this clinical study a medication error is an **unintended** failure or mistake in the treatment process for an IMP or AstraZeneca Non Investigational Medicinal Product that either causes harm to the participant or has the potential to cause harm to the participant.

The full definition and examples of medication error can be found in Appendix B 8.

8.4.4.2 Drug Abuse

Drug abuse is the persistent or sporadic **intentional**, non-therapeutic excessive use of IMP or AstraZeneca NIMP for a perceived reward or desired non-therapeutic effect.

The full definition and examples of drug abuse can be found in Appendix B 8.

8.4.4.3 Drug Misuse

Drug misuse is the **intentional** and inappropriate use (by a study participant) of IMP or AstraZeneca NIMP for medicinal purposes outside of the authorised product information, or

for unauthorised IMPs or AstraZeneca NIMPs, outside the intended use as specified in the protocol and includes deliberate administration of the product by the wrong route.

The full definition and examples of drug misuse can be found in Appendix B 8.

8.4.5 Management of IP-related toxicities Dose Modification

Dose Modification Management of IP-related toxicities can be found in Section [6.6](#).

8.5 Pharmacokinetics

8.5.1 Collection of pharmacokinetic samples

In Phase 1 portion, venous blood samples for determination of concentrations of acalabrutinib and its metabolite (ACP-5862) in plasma will be taken at the times presented in [Table 11](#) and [Table 12](#). The date and time of collection of each sample will be recorded.

The timing of the pharmacokinetic samples may be adjusted during the study, dependent on emerging data, in order to ensure appropriate characterization of the plasma concentration-time profiles.

Table 11 Pharmacokinetic sampling schedule (Single dose, Phase 1 portion)

Cycle	Day	Pre-dose***	Hours Post-dose										
			0.25 (±1min)	0.5 (±5min)	0.75 (±5min)	1*	2*	4*	6*	8*	12*	24*	48*
0	1	X	X	X	X	X	X	X	X	X	X	X	X**

* Time allowance: ±10 min

** Before Cycle 1 Day 1 morning dose

*** Within 10 min prior to dosing

Table 12 Pharmacokinetic sampling schedule (Multiple doses, Phase 1 portion)

Cycle	Day	Pre-dose***	Hours Post-dose								
			0.25 (±1 min)	0.5 (±5 min)	0.75 (±5 min)	1*	2*	4*	6*	8*	12*
1	8	X	X	X	X	X	X	X	X	X	X**
1	28					X (±0.5 hr)	X (±0.5 hr)	X (±1 hr)			

* Time allowance: ±10 min

** Before Cycle 1 Day 8 evening dose

*** Within 10 min prior to dosing

In Phase 2 portion, the schedule of sparse PK sampling for determination of acalabrutinib plasma concentration is presented in [Table 13](#).

Table 13 Sparse pharmacokinetic sampling schedule in Phase 2 portion

Cycle	Day	Hours Post-dose		
		1 (\pm 0.5 hr)	2 (\pm 0.5 hr)	4 (\pm 1 hr)
1	8	X	X	X
1	15 or 22	X	X	X

All timepoints are relative to the morning dose.

Samples will be collected, labelled, stored and shipped as detailed in the Laboratory Manual.

8.5.2 Determination of drug concentration

Samples for determination of acalabrutinib concentration in plasma will be analyzed by analytical test sites on behalf of AstraZeneca, using an appropriate bioanalytical method. Full details of the analytical method used will be described in a separate bioanalytical report.

8.5.3 Storage and destruction of pharmacokinetic samples

Pharmacokinetic (PK) samples will be disposed of 6 months within final Bioanalytical Report publication.

Incurred sample reproducibility analysis, if any, will be performed alongside the bioanalysis of the test samples. The results from the evaluation will not be reported in the CSR but separately in a Bioanalytical Report.

8.6 Pharmacodynamics

Pharmacodynamic parameters are not evaluated in this study.

8.7 Genetics

Genetic testing is not evaluated in this study.

8.8 Biomarkers

Biomarkers are not evaluated in this study.

8.9 Health Economics

Health Economics parameters are not evaluated in this study.

9. STATISTICAL CONSIDERATIONS

9.1 Statistical hypotheses

Refer to Section 9.2 for details.

9.2 Sample size determination

The primary objectives of Phase 1 portion are to evaluate the safety, tolerability and pharmacokinetics (PK) of acalabrutinib. Hence approximately 12 subjects will be enrolled in Phase 1 to obtain adequate pharmacokinetic and safety data. Additional subjects may be enrolled to ensure at least 8 eligible subjects for evaluable single- and multiple-dose PK profiles based on China regulatory considerations.

For Phase 2 of the study, approximately 33 R/R MCL subjects (Cohort A) and 60 R/R CLL subjects (Cohort B) will be enrolled in order to evaluate the efficacy in R/R MCL and R/R CLL subjects. For Cohort A, a sample size of 33 subjects will provide a 95% two-sided confidence interval centered around an expected ORR of 80% that excludes an ORR of 60% as a lower bound. With 60 subjects from Cohort B, an exact binomial test with a nominal one-sided 2.5% significance level will have 90% power to detect the difference between a null hypothesis ORR of 70% and an alternative ORR of 88%.

9.3 Populations for analyses

For purposes of analysis, the following populations are defined:

Analysis set	Description
Safety analysis set	All subjects who received at least 1 dose of acalabrutinib.
Pharmacokinetics analysis set	Dosed subjects with reportable acalabrutinib plasma concentration and PK parameter data with no important protocol deviations that may impact PK.
Tumor response analysis set	Dosed subjects with a relevant baseline tumor assessment.

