2. ANALYSIS SETS

2.1. Definition of analysis sets

For purposes of analysis, the following populations are defined:

Analysis set	Description
Safety analysis set	All subjects who received at least one dose of acalabrutinib.
Pharmacokinetics analysis set	All subjects who received at least one dose of acalabrutinib, for whom with reportable acalabrutinib plasma concentration and PK parameter data with no important protocol deviations that may impact PK.
Tumor response analysis set	All subjects who received at least one dose of acalabrutinib and for whom baseline tumor assessment is available.

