2.2. Protocol deviations

For this study, the following general categories will be considered important protocol deviations (IPDs) and most of them (programmable IPDs) will be programmatically derived from the electronic case report form (eCRF) data. Few observable IPDs may only be identified by site monitoring activities as the data is not captured in any clinical data base.

- Inclusion criteria deviations
- Exclusion Criteria Deviations
- Discontinuation Criteria for study product met but participant not withdrawn from study treatment

- Discontinuation Criteria for overall study withdrawal met but patient not withdrawn from study
- Investigational Product (IP) deviation
- Excluded medications taken
- Deviations to study procedure
- Other Important Deviations

IPD categories are defined and managed by the study team during the IPD reviews throughout the study before database lock. These definitions of IPD categories, sub-category codes, and descriptions will be used during the course of the study. The final IPD list is used to produce the Summary of IPDs output and the Listing of Subjects with IPDs. No deviations will lead to patients being excluded from the analysis sets described in Section 2.1 (with the exception of the pharmacokinetics analysis set, if the deviation is considered to impact upon PK).

A per-protocol efficacy analysis excluding patients with significant protocol deviations is not planned. However, a 'deviation bias' sensitivity analysis may be performed on the ORR endpoint excluding patients with deviations that may affect the efficacy of the trial therapy if >10% of patients in either cohort of Phase 2 portion: Did not have the intended disease or indication.

The need for such a sensitivity analysis will be determined following review of the protocol deviations ahead of database lock and will be documented prior to the primary analysis being conducted.

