4.2.6. Pharmacokinetic analyses

All PK analyses will be summarized based on the PK analysis set. The data excluded from the PK analysis set will be flagged in subject listing only.

Precision and rounding rules for pharmacokinetic data

For PK concentration data, the listings will be presented to the same number of significant figures as the data received from the bioanalytical laboratory; for PK parameters, the listings will be presented according to the following rules:

- Cmax, Cmin – will be presented to the same number of significant figures as received from the bioanalytical laboratory.
- tmax, λz lower and upper time limit – will be presented as received in the data, usually to 2 decimal places
- AUCinf, AUClast, AUC0-12, AUC τ , $t_{1/2}\lambda z$, CL/F, Vz/F, Rac ratios, metabolite to parent ratios, Rsq, Rsq adj, λz span ratios – will be presented to 3 significant figures
- λz – will be presented to 4 significant figures
- λz , N – will be presented as an integer (no decimals)
- Tlast - will be presented as received in the data, usually to 2 decimal places

- AUCextr – will be presented to 3 significant figures

For PK concentration data all descriptive statistics will be presented to 4 significant figures with the exception of the minimum and maximum which will be presented to 3 significant figures.

For PK parameter data the descriptive statistics will be presented according to the following rules:

- Cmax, Cmin, AUCinf, AUClast, AUC0-12, AUC τ , $t^{1/2}\lambda_z$, CL/F, Vz/F, Rac ratios and metabolite to parent ratios descriptive statistics will be presented to 4 significant figures with the exception of the minimum and maximum which will be presented to 3 significant figures
- tmax – all descriptive statistics will be presented as received in the data, usually to 2 decimal places
- λ_z – all descriptive statistics will be presented to 5 significant figures with the exception of the minimum and maximum which will be presented to 3 significant figures

Source data shall be used in all derived PK parameter calculations without prior rounding.

Phase 1 portion

Plasma concentrations of acalabrutinib and a metabolite (ACP-5862) will be summarized by nominal sample time. Plasma concentrations at each time point will be summarized by the following summary statistics:

- The geometric mean (gmean, calculated as $\exp[\mu]$, where μ is the mean of the data on a logarithmic scale)

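### The PK analysis set excludes whole subjects, so an important PK-affecting deviation confined to one sampling day also drops that subject's valid profiles from other days

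*Protocol*

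**What the plan says.** Protocol 9.3 describes the PK analysis set as dosed subjects with "reportable acalabrutinib plasma concentration and PK parameter data with no important protocol deviations that may impact PK". SAP 2.1 carries the same condition, again as a property of the subject: "with reportable acalabrutinib plasma concentration and PK parameter data with no important protocol deviations that may impact PK".

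SAP 2.2 then states the consequence: "No deviations will lead to patients being excluded from the analysis sets described in Section 2.1 (with the exception of the pharmacokinetics analysis set", the exception applying where the deviation is judged to affect PK. SAP 4.2.4.1 plans a table counting the subjects excluded from each analysis set. SAP 4.2.6 makes the set govern the results: "All PK analyses will be summarized based on the PK analysis set".

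Phase 1 samples on three occasions (Protocol 8.5.1): a single-dose profile on Cycle 0 Day 1, a 12-hour steady-state profile on Cycle 1 Day 8, and three sparse samples on Cycle 1 Day 28. Parameters are derived from the first two days only (Protocol 9.4.1.2, SAP 3.2.3). Single- and multiple-dose parameters are summarized separately (Protocol 9.4.3, SAP 4.2.6).

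On numbers, Protocol 9.2 says "approximately 12 subjects will be enrolled in Phase 1 to obtain adequate pharmacokinetic and safety data" and adds "Additional subjects may be enrolled to ensure at least 8 eligible subjects for evaluable single- and multiple-dose PK profiles".

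**The concern.** The unit of exclusion does not match the unit of analysis. The tables are built by sampling occasion, while the exclusion removes the person. A deviation that spoils one day takes the other days with it, and no sentence in either document brings them back.

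One-day deviations are plausible. Fasting is required only for the morning doses of Cycle 0 Day 1 and Cycle 1 Day 8 (Protocol 6.1.1). The important-deviation categories in SAP 2.2 include excluded medications and departures from study procedures. PK characterization is a primary Phase 1 objective, and with about 12 subjects each discarded valid profile is a visible share of the data.

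**Working it through.** **1. Which faults reach the subject-level rule.**
- A missing or out-of-window concentration is left out of the tables and mean plots individually, flagged, and kept in the individual plots (SAP 4.2.6). The subject stays in.
- A parameter that cannot be determined for lack of concentrations is shown as not calculated (SAP 4.2.6). The subject stays in.
- A correctly timed, quantifiable sample affected by an important deviation is covered by neither rule. It falls to SAP 2.2, and the patient leaves the set.
- SAP 4.2.6 also says that data excluded from the PK set are flagged in listings. That governs display and does not return an unaffected day to the summaries.

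**2. Whether the other days remain valid.** A later deviation cannot change an earlier profile, so a Day 8 or Day 28 problem leaves Cycle 0 Day 1 intact. In the other direction, Protocol 2.2.3.3 gives acalabrutinib a half-life of about 1 hour and no accumulation, so a food breach on Cycle 0 Day 1 has no evident route to the parent drug's profile on Cycle 1 Day 8. An excluded drug taken early could still act later, so the test should be whether PK on that day may have been affected. A Day 28-only deviation touches no derived parameter, yet the literal rule removes the subject from both parameter tables.

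**3. The plan's own figures.** The 12 enrolled and at least 8 evaluable rest on regulatory considerations. No variance, precision target or formula is given, so there is nothing to reproduce.

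**4. Illustrative precision cost.** Assume that two of 12 subjects have a deviation confined to another day, and that the SD is unchanged. The log-scale 95% half-width, in SD units, is t(0.975, n−1)/√n:
- n = 12: 2.201/3.464 = 0.635
- n = 10: 2.262/3.162 = 0.715
- ratio: 0.715/0.635 = 1.13, or +13%

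As a multiplicative factor on a geometric mean, exp(t·s/√n) with s = √ln(1+CV²), for CVs that are assumed because the documents give none:

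| Assumed CV | n = 12 | n = 10 |
|---|---|---|
| 30% | 1.205 | 1.234 |
| 50% | 1.350 | 1.402 |
| 70% | 1.494 | 1.571 |

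**5. Illustrative count of usable profiles.** Let q be an assumed, independent chance of a qualifying deviation on each of the two intensive days. Expected usable subjects per day are 12(1−q)² under whole-subject exclusion and 12(1−q) under exclusion by day:

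| q | Whole subject | By day | Difference |
|---|---|---|---|
| 5% | 10.8 | 11.4 | 0.6 |
| 10% | 9.7 | 10.8 | 1.1 |
| 20% | 7.7 | 9.6 | 1.9 |

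**The case against.** The case for leaving the text alone has real force.

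- **The trigger is narrow.** The deviation must be important and judged to affect PK, "with the exception of the pharmacokinetics analysis set, if the deviation is considered to impact upon PK", and categories are reviewed before database lock. A reader might infer that any fault on a PK day costs the subject. The documents do not support that, and the commonest faults are handled sample by sample.
- **A common subject set is a legitimate choice.** The accumulation ratios and the temporal change parameter need both intensive days, so exclusion by day gains nothing for them. This stands, but those parameters can require both days without imposing that condition on the separate single- and multiple-dose tables.
- **The wording is mixed.** SAP 4.2.6 refers to excluded data, so the authors may have meant exclusion by day. That is possible, but both set definitions, SAP 2.2 and the SAP 4.2.4.1 table are all expressed by subject or patient.
- **Replacement subjects.** A reader might infer that the rule forces needless top-up enrolment. For a Day 8 deviation it does not: the floor of 8 requires both profiles, and that subject lacks a valid multiple-dose profile under either rule. Only a Day 28-only deviation could prompt an unnecessary replacement, and only if evaluability is tied to membership of the PK set, which the documents do not state.
- **No inference is at risk.** PK is summarized descriptively and no confidence interval is planned. This stands, and it limits the precision figures to a measure of information lost.

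**Conclusion.** The point holds as a minor, inexpensive improvement. As written, an important deviation considered to affect PK removes the whole subject even when it is confined to one PK day, and valid data from unaffected days drop out of separately presented tables. Neither the flagging sentence nor the per-sample rules restore them.

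The size is conditional. A 13% wider log-scale half-width for the unaffected day follows if two of 12 subjects have such a deviation. That number is assumed, and the cost is nil if no such deviation occurs. A reader might set the precision at 8 subjects against that at 12 and call the gap the damage, but 8 is the protocol's own accepted minimum and is not a loss caused by this rule. Nor do the documents show any bias in the exposure estimates. The argument concerns avoidable loss of valid data.

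**What to change.** Add to Protocol 9.3 and SAP 2.1, and align SAP 2.2: concentrations and parameters from a PK sampling day are excluded if an important deviation may have affected PK on that day; the same subject's unaffected days stay in the PK analysis set; Rac AUC, Rac Cmax and TCP are derived only when both Cycle 0 Day 1 and Cycle 1 Day 8 are valid. The day-by-day decision should be recorded at the deviation review before database lock. If whole-subject exclusion is intended, the SAP should say so and give the reason.

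The cost is a few lines of text and an n that may differ between the single- and multiple-dose tables. The number of observations is already among the planned statistics, and the existing per-sample and not-calculated rules already allow n to vary.
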